4.12 Pharmacodynamics and Pharmacokinetics

4.12.1 Analysis and Data Conventions

This study aims to demonstrate that AZD9567 improves glucose homeostasis compared to oral prednisolone.

The null hypothesis for the primary analysis is:

H₀: there is no difference in the change in glucose AUC(0-4) versus baseline in AZD9567 compared to prednisolone following a standardised MMTT.

The alternative hypothesis for the primary analysis is:

H_a: there is a difference in the change in glucose AUC(0-4) versus baseline in AZD9567 compared to prednisolone following a standardised MMTT.

In order to test the null hypothesis, a main analysis involving the FAS will be conducted. If more than 10% of participants receive the wrong treatment, a sensitivity analysis involving the PP will be conducted.

The following comparison will be performed:

- 72 mg AZD9567 versus 40 mg prednisolone (Cohort 1)
- 40 mg AZD9567 versus 20 mg prednisolone (Cohort 2)
- Placebo versus 5 mg prednisolone (Cohort 3)

As this is a Phase 2a study, no adjustments for multiple testing will be performed.

4.12.1.1 Multi-center Studies

No adjustments for center will be performed.

4.12.1.2 Handling of Dropouts or Missing Data

Summary statistics will be based on non-missing values.

4.12.1.3 Interim Analyses

Two interim analyses are planned.

The first interim analysis will be conducted when 50% of the participants in Cohort 1 have completed the study. The purpose of the first interim analysis is to evaluate the feasibility of the assumptions and conduct sample size re-estimation if required.

The main objective of the first interim analysis is to report the statistical analyses involving the first endpoint, the secondary endpoints related to glucose (mean daily glucose at 48-72 hours treatment and rise in mean daily glucose over 24-hour periods from start of IMP dosing) and the safety endpoints (AEs/SAEs) for 50% of the subjects in Cohort 1.

The second interim analysis will be conducted when all the participants in Cohort 1 have completed the study. The main objective of the second interim analysis is to report the statistical analyses involving all subjects in Cohort 1.

The second interim analyses will not include PK data.

4.12.2 Pharmacodynamics

All the models presented in this section will be analysed with unstructured covariance structure used for the within-participant errors. In the case of a model which does not converge, the analysis will be performed with a Toeplitz covariance structure and, in case of non-convergence, it will be performed with a compound symmetry structure.

Primary endpoint

The primary endpoint is the change in glucose AUC(0-4) and will be summarised by timepoint (baseline and Day 4) and by each cohort. The comparison of the change in glucose AUC(0-4) (where change from baseline in glucose AUC is assumed to be normally distributed) between the two treatments administered within each cohort after a standardised MMTT will be performed by means of two linear mixed effects models, with an unstructured covariance structure, with treatment, period and sequence as fixed effects, participant within sequence as random effect and baseline as covariate.

Two models will be run separately for each cohort:

1. In the first model, the dependent variable will be the change from baseline in AUC(0-4) whereas the AUC(0-4) on Day -1 will be included as a covariate. The treatment effects will be estimated by the Least Square means (LS means) and their 95% CIs and the difference between the two treatments by the difference in LS means with its 95% CI.

2. The second model will involve the following three steps:

a) Log-transformation of the AUC(0-4):

First, the AUC(0-4) in Day -1 and the AUC(0-4) in Day 4 will be log-transformed. The log-transformed AUC(0-4) in Day -1 will then be subtracted from the log-transformed AUC(0-4) in Day 4 to calculate the change in AUC (0-4) in log units.

b) Execution of the model:

The model will include the change in AUC (0-4) in log units as a dependent variable and the log-transformed AUC(0-4) in Day -1 as covariate.

c) Back-transformation of the results from the model:

The results from the execution of the model will be back transformed to the original scale after an exponentiation of the means and CIs estimated by the model to obtain the percentage geometric LS means of the treatments and their percentage SEs. The LS mean difference and its CI between the two treatments will also be back-transformed to yield the percentage geometric mean ratio between the two treatments with its 95% CI at Day 4.

The statistics for the percentages geometric LS means, percentage SE, percentage geometric LS mean ratio and percentage 95% CI will be calculated as follows:

i) Percentage geometric LS mean = $(\exp(\text{estimate})-1)*100$ where estimate is the natural log of LS mean

ii) Percentage SE = $\text{sqrt}(\exp(2*\text{estimate})*\text{SE}^2)*100$

iii) Percentage geometric LS mean ratio = $(\exp(\text{estimate})-1)*100$ where estimate = log LS mean difference

iv) percentage 95% CI lower and upper: $(\exp(\text{lower})-1)*100$; $(\exp(\text{upper})-1)*100$.

If more than 10% of participants are treated erroneously, a sensitivity analysis will be carried out using the actual treatment received instead. Descriptive statistics and graphical presentations will be presented.

The following graphs will be provided:

- Line plot: the Mean glucose levels (MMTT) by sampling time in minutes by treatment -visit day; (per cohort)
- AUC(0-4) change from baseline (MMTT) for glucose level by visit day of linear mixed model (Full Analysis Set) (all cohorts in a single plot)

- AUC(0-4) percentage change from baseline (MMTT) for glucose level by visit day linear mixed model (Full Analysis Set) (all cohorts in a single plot).

The following comparison will be performed by the execution of a linear mixed effects model in each case:

- 72 mg AZD9567 versus 40 mg prednisolone (Cohort 1)
- 40 mg AZD9567 versus 20 mg prednisolone (Cohort 2)
- placebo versus 5 mg prednisolone (Cohort 3).

Secondary endpoints

Mean daily glucose at 48-72 hours (CGM)

The Mean daily glucose (CGM) as well as the change from baseline will be summarize by timepoint (baseline, 00-24 h, 24-48 h and 48-72 h) and by treatment group.

The comparison of the effect of the two treatments on the mean daily glucose at 48-72 measured by CGM will be analysed by means of repeated measures mixed model (MMRM) with treatment + time (0-24h, 24-48h, 48-72h), treatment*time, period and sequence as fixed effects with baseline (mean glucose at -24-0 hours) as covariate and participants within sequence as random effect. Two models will be run separately for each cohort and will be:

1. In the first model, the dependent variable will be the mean daily glucose whereas the mean glucose at -24-0 hours will be included as covariates. The treatment effects will be estimated as described in the first model for the primary endpoint.
2. The second model will involve a log-transformation of both the mean glucose at 0-24, 24-48 and 48-72 hours and the mean glucose at -24-0 hours will be included as a covariate. The treatment effects will be estimated as described in the second model for the primary endpoint.

The following graphs will be provided:

- Glucose mean levels (CGM) at 0-72 h by treatment (per cohort)
- Glucose mean levels (CGM) at 0-72 h by treatment (all cohorts in a single plot).

Rise in mean glucose at 00-24 h, 24-48h and 48-72 h (CGM)

The comparison of the effect of the two treatments on the rise in mean glucose at 0-24, 24-48 and 48-72 hours will be performed following two different approaches:

- 1) In the first approach three different models will be performed:
 - i) Change at 00-24 h from baseline (24 hours of CGM prior to dosing) performed by means of mixed models with treatment, period and sequence as fixed effects, participants within sequence as random effect and baseline mean glucose
 - ii) Change at 24-48 h from baseline (24 hours of CGM prior to dosing) performed by means of mixed models with treatment, period and sequence as fixed effects, participants within sequence as random effect and baseline mean glucose
 - iii) Change at 48-72 h from baseline (24 hours of CGM prior to dosing) performed by means of mixed models with treatment, period and sequence as fixed effects, participants within sequence as random effect and baseline mean glucose.
- 2) In the second approach three different models will be performed:
 - i) Change at 00-24 h from baseline (24 hours of CGM prior to dosing) performed by means of mixed models with treatment, period and sequence as fixed effects, participants within sequence as random effect and baseline mean glucose
 - ii) Change at 24-48 h from baseline (00-24 h) performed by means of mixed models with treatment, period and sequence as fixed effects, participants within sequence as random effect and baseline mean glucose
 - iii) Change at 48-72 h from baseline (24-48h) performed by means of mixed models with treatment, period and sequence as fixed effects, participants within sequence as random effect and baseline mean glucose.

The three models for each of the approaches were repeated considering the log-transformation of the dependent variable to obtain the Geometric LS means and the Geometric LSMean Ratio (%).

The following comparison will be performed for the change and the percent change from baseline at 0-24, 24-48 and 48-72 hours:

- 72 mg AZD9567 versus 40 mg prednisolone (Cohort 1)
- 40 mg AZD9567 versus 20 mg prednisolone (Cohort 2)
- placebo versus 5 mg prednisolone (Cohort 3).

The following graphs will be provided:

- Rise in mean change from baseline (CGM) for glucose by Days (Day -1 (24 h prior to dosing), Day 1 (00-24 h), Day 2(24-48 h), Day 3(48-72 h)) 1st approach (per cohort)

- Rise in mean change from baseline (CGM) for glucose by Days (Day -1 (24 h prior to dosing), Day 1 (00-24 h), Day 2(24-48 h), Day 3(48-72 h)) 2nd approach (all cohorts in a single plot)
- Rise in mean percentage change from baseline (CGM) for glucose by Days (Day -1 (24 h prior to dosing), Day 1 (00-24 h), Day 2(24-48 h), Day 3(48-72 h)) 2nd approach (all cohorts in a single plot).

Change from baseline in fasting glucose

The comparison of the effect of the two treatments on the change from baseline in fasting glucose (-15 minutes) between Days -1 and 4 will be performed by the same model as that for the comparison of the primary endpoint.

The following comparison will be performed for the change and the percent change from baseline at Day 4:

- 72 mg AZD9567 versus 40 mg prednisolone (Cohort 1)
- 40 mg AZD9567 versus 20 mg prednisolone (Cohort 2) placebo versus 5 mg prednisolone (Cohort 3).

Changes in in AUC(0-4) in hormones, FFAs and C-peptide in response to a MMTT

The comparison of the effect of treatment on changes in insulin, glucagon, GLP-1, GIP, FFAs and C-peptide will be analysed as the primary endpoint.

The following graphs will be provided for each of the variable with the exception of C-peptide:

- The changes from baseline at different timepoints by treatment (all cohorts in a single plot)
- The percentage changes from baseline at different timepoints by treatment (all cohorts in a single plot).

MMTT derived first phase insulin response

The ratio between variables will be calculated based on the following steps:

- Calculate ΔI_{10} = difference in I (insulin) values between 10 and 0 minutes at Day -1 and Day 4 of each period

- ii) Calculate ΔG_{10} = difference in G (glucose) values between 10 and 0 minutes at Day-1 and Day 4 of each period
- iii) Calculate the ratio $\Delta I_{10} / \Delta G_{10}$ at Day-1 and Day 4 of each period.

The same steps i) to iii) accordingly to timepoints 10 and 30, will be performed for $\Delta C_{10} / \Delta G_{10}$, $\Delta I_{30} / \Delta G_{30}$, and $\Delta C_{30} / \Delta G_{30}$.

The comparison of the effect of the two treatments on the change in $\Delta I_{10} / \Delta G_{10}$ and $\Delta I_{30} / \Delta G_{30}$, between Days -1 and 4 will be performed by the same model as that for the comparison of the primary endpoint.

The following comparison will be performed for the change from baseline and the percent change from changes from baseline at Day 4 at 10 and 30 minutes:

- 72 mg AZD9567 versus 40 mg prednisolone (Cohort 1)
- 40 mg AZD9567 versus 20 mg prednisolone (Cohort 2)
- placebo versus 5 mg prednisolone (Cohort 3).

The previous analyses will be repeated for the comparison of the effect of the two treatments on the change in $\Delta C_{10} / \Delta G_{10}$, $\Delta C_{30} / \Delta G_{30}$ using C-peptide instead of insulin in the calculation of these ratios.

HOMA-IR and HOMA-S

A summary of the baseline HOMA-IR and HOMA-S and at Day 4 as well as change from baseline, will be provided by treatment.

24-hour U-Na and U-K

The 24-hour Na and K concentration and its ratio (Na/K) in urine will be analysed as the primary endpoint.

The following comparisons will be performed for the change and percentage change from baseline at 0-24 hours on Day 3:

- 72 mg AZD9567 versus 40 mg prednisolone (Cohort 1)
- 40 mg AZD9567 versus 20 mg prednisolone (Cohort 2)
- placebo versus 5 mg prednisolone (Cohort 3).

TNF α concentrations

Descriptive statistics will be tabulated for the individual measurement points of the LPS-stimulated TNF α levels.

An ANOVA model with treatment, sequence and subject as random effect will be run separately for each cohort (Cohort 1 and Cohort 2) for the comparisons of the treatments at Day 3.

A scatter plot of individual plasma concentrations of AZD9567 (nmol/L) in a log scale on the X axis versus individual LPS-Stimulated TNF α Levels (ng/L) in log scale on the Y axis will be created.

CCI

[Redacted content]

CCI

CONFIDENTIAL

Project Document Version No. Final 2.0

Project Document Effective Date: <Date of last signature>

CCI [REDACTED]

[REDACTED]

[REDACTED]

[REDACTED]

[REDACTED]

[REDACTED]

[REDACTED]

[REDACTED]

Calculations of endpoints analysed by statistical models

Calculation of changes from baseline AUC (0-4)

The calculation of the change in glucose, insulin, C-peptide GLP-1, GIP, glucagon and FFAs AUC(0-4) will involve the following steps:

1. The AUC(0-4) each day when the MMTT is consumed will be calculated by means of the linear-log trapezoidal method, i.e., using the linear trapezoidal method when concentrations are increasing and the logarithmic trapezoidal method when concentrations are decreasing.

Accordingly, for a given time interval ($t_1 - t_2$), the AUC could be calculated as follows:

i) by the linear trapezoidal method:

$$AUC = 1/2 (C_1 + C_2) (t_2 - t_1)$$

ii) by the logarithmic trapezoidal method:

$$AUC = [(C_1 - C_2) / (\ln(C_1) - \ln(C_2))] (t_2 - t_1)$$

where:

CCI [REDACTED]

- C_1 and C_2 are the concentrations at times 1 (t_1) and 2 (t_2).the first time interval ($t_1 - t_2$) is equal to t_1 (ie, the concentration at -15 minutes is assumed to be the same as if it had been made at 0 minutes),
- for assessments at 10, 20, 30, 60, 75, 120 and 180 minutes, t_1 and t_2 are actual times,
- for the planned assessment at 240 minutes, the planned time (240) will be used if such an assessment has been performed within the allowed time window (± 5 minutes).

The total AUC between 0 and 240 minutes will be calculated as the sum of the AUC for each of the intervals described in i) and ii).

The total AUC between two time points will be calculated as the sum of the AUCs calculated for each of the intervals between the two time points.

2. The change in AUC(0-4) will be calculated as:

$$\Delta \text{AUC}(0-4) = \text{AUC}(0-4) \text{ at Day 4} - \text{AUC}(0-4) \text{ at Day -1}$$

For the calculation of MMTT $\text{AUC}_{0-4\text{hr}}$, the pre-meal measurement (at -15 min) value will be treated as the value at the meal time (0 minutes). The actual time span for each post-meal measure will be calculated starting from the meal time (0 minutes). If any actual sample collection times are missing, use the scheduled nominal times with reference to the actual meal time to impute.

If the actual sampling times differ from the nominal times more or equal to $|5|$ min, this will be deemed on case-by-case basis if should be considered protocol deviation.

If greater than 50% of scheduled measures are missing, the AUC will be set as missing; if the first two or last two scheduled measures are both missing, then the AUC will also be set as missing; otherwise:

For all the MMTT endpoints (glucose, insulin, glucagon, GLP-1, GIP, FFAs and C-peptide):

If any interior measures are missing, the trapezoid rule can be used to calculate the AUC by ignoring the missing time point: i.e. The missing timepoint X will be imputed with the value obtained considering the linear interpolation between the last actual assessment taken prior to point X, and the first actual assessment taken after point X.

For glucose MMTT endpoint:

- If the pre-meal value is missing, set the missing value = 92% of the value for next scheduled time point.
- If the last value is missing, set the missing value = 87% of the value for the time point that is scheduled immediately prior to the last time point.

For the rest of MMTT endpoints (insulin, glucagon, GLP-1, GIP, FFAs and C-peptide):

- If the pre-meal value is missing, set AUC = missing
- If the last value is missing, set AUC = missing

AUC(0 -4h) calculation assumes that measurements are available at 240 min exactly. Deviation from 240 min will induce a systematic overestimation of the actual value of the sampling time is used exceeds 240 min and underestimation of the actual time is under 240 min. If the deviation is within the allowance window (± 5 min) the sampling time will be equated to 240 min. If the sampling time for the 240 min measurement is out of the sampling window (± 5 min) a linear interpolation will be considered to assess the value at 240 min using the actual sampling times for the 180 min and the 240 min measurements.

Actual time point (at 180 min) and the time point for last sampling will be defined with t_{180} and with t_{last} respectively, and the values of the endpoint (glucose, insulin etc) at the actual measured timepoint and at time point for the last sampling will be defined with y_{180} and y_{last} . From the available information (t_{180}, y_{180}), (t_{last}, y_{last}) the value at t_{240} , i.e. the value that the endpoint would have if we would have taken the sample at exactly 240 min from start will be interpolated. Interpolation assumes a linear equation with slope

$$m = (y_{last} - y_{180}) / (t_{last} - t_{180})$$

and intercept

$$b = \text{mean}(y_{last}; y_{180}) - m * \text{mean}(t_{last}; t_{180})$$

giving the value at 240 minutes of:

$$y_{240} = b + m * 240.$$

The 92 % and 87 % correction factors were based on the MEDI0382 (D5670C00007) study.

Calculation of HOMA-IR

The HOMA-IR will be calculated as follows based on glucose and insulin measured prior to MMTT (-15 min):

$$\text{HOMA - IR} = \frac{\text{Glucose} \left(\frac{\text{mmol}}{\text{L}} \right) \times \text{Insulin (mU/L)}}{22.5}$$

HOMA-S will be calculated as the reciprocal of HOMA-IR.

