### 1.3.1 Blood Sampling Schedule for Mixed Meal Tolerance Tests (MMTTs)

	Day -1, Day 4, Day 27, and Day 31 (minutes)	Comments
Plasma glucose, insulin, C-peptide GLP-1, GIP, glucagon, and FFAs	-15, 10, 20, 30, 60, 75, 120, 180, 240	Time point in relation to the start of the meal

Abbreviations: FFA: free fatty acid; GLP-1: glucagon-like peptide-1; GIP: glucose-dependent insulin releasing polypeptide

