### **8.2.2 Mixed Meal Tolerance Test (MMTT)**

On Days -1, 4, 27, and 31, a standardised mixed meal (meal should be consumed as fast as the participant can, within 30 minutes) will be administered in the morning, around 0700, after an overnight fast of 12 hours. Blood samples will be taken according to the schedule in Section 1.3.1 for analysis of glucose, insulin, C-peptide, GLP-1, glucose-dependent insulin releasing polypeptide (GIP), glucagon and FFAs.

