4.8 Baseline, change from baseline and percentage change from baseline definitions

Demography and baseline characteristics

For demography and baseline characteristics other than weight, the baseline will be the assessment at screening. For weight, the baseline will be the assessment at Day -1 performed by means of the **CCI** device. If the weight at Day -1 is missing, the weight at Day -2 (or at Screening, in the case of period 1 if the value at Day -2 is also missing) will be the baseline for such a period.

Pharmacodynamics

Change in AUC(0-4)

In the case of the linear mixed models for the change from baseline in glucose AUC(0-4) (primary endpoint), hormones related to glucose homeostasis (insulin, glucagon, GLP-1, GIP), FFAs and C-peptide (secondary endpoints), the baseline measurement will be the AUC(0-4) on Day -1 (i.e., prior to first dosing) of each period.

Glucose concentrations assessed by CGM

For the calculation of the rise in mean glucose and the mean daily glucose, the baseline will be the average of the values from -24 hours to first dosing on Day 1 (values from -72 to -24 hours will be excluded from the baseline) of each period.

For the MMRM for the rise in mean glucose and the mean glucose, the baseline included as a covariate in the model will be the value -24 hours to first dosing on Day 1 of each period.

MMTT derived first phase insulin response

For the calculation of the change from baseline of insulin, glucose and C-peptide included in the calculation of $\Delta I10/\Delta G10$, $\Delta I30/\Delta G30$, $\Delta C10/\Delta G10$ and $\Delta C30/\Delta G30$, the baseline will be value at Day -1 of each period.

24-hour U-Na and U-K

For Na and K and the Na/K ratio, the baseline will be the value at Day -1 in each period.

CCI [Redacted]

[Redacted]

[Redacted]

[Redacted]

[Redacted]

[Redacted]

[Redacted]

[Redacted]

[Redacted]

Safety

ECG and vital signs

For ECG and vital signs, the baseline will be the pre-dose assessment at Day 1 in each period. If this value is missing the value closest in time prior to Day 1 within the same visit (or at Screening, in the case of period 1) will be the baseline for such a period.

Clinical chemistry/haematology/urinalysis

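### The first-phase ratios ΔI/ΔG and ΔC/ΔG have inconsistent baseline definitions and are sent to a normal and a log model that do not suit a ratio of two differences, chiefly at 10 minutes

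*SAP*

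**What the plan says.** **Definition in SAP 4.8.** The baseline section covers the components of the ratios: "For the calculation of the change from baseline of insulin, glucose and C-peptide included in the calculation of" the four ratios, "the baseline will be value at Day -1 of each period". Read literally, each Δ is a Day 4 value minus a Day -1 value.

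**Definition in SAP 4.12.2.** Under the first-phase insulin response, ΔI10 is the "difference in I (insulin) values between 10 and 0 minutes at Day -1 and Day 4 of each period" and ΔG10 is the "difference in G (glucose) values between 10 and 0 minutes at Day-1 and Day 4 of each period". A ratio is formed on each day. For the other ratios: "The same steps i) to iii) accordingly to timepoints 10 and 30, will be performed for" them. Here Δ is a rise within one meal test.

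**Model.** The comparison of the change in the ratio "between Days -1 and 4 will be performed by the same model as that for the comparison of the primary endpoint", and the C-peptide ratios are treated alike. The primary-endpoint analysis is a pair: an untransformed mixed model for the change, and a model on log Day 4 minus log Day -1. SAP 4.12.2 also asks for percent change in the ratios, so the log model appears to be intended.

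**Sampling.** Protocol 1.3.1 times the samples as "Time point in relation to the start of the meal", at -15, 10, 20, 30 minutes and later. There is no 0-minute sample. Protocol 8.2.2 says the "meal should be consumed as fast as the participant can, within 30 minutes".

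**What is absent.** Neither document has a rule for ΔG at, near or below zero, or for the log of a non-positive ratio. SAP 4.3.2 leaves missing data unimputed unless otherwise stated.

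**The concern.** The two sections give Δ different meanings, so two programmers could derive different variables from the same samples.

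The more substantial issue is the model. Glucose AUC(0-4) is always positive, so its log exists. A ratio of two differences has no such guarantee. If the 10-minute glucose is at or slightly below the pre-meal value, ΔI10/ΔG10 is undefined, very large, or negative. A negative denominator also reverses the meaning: a good insulin rise with a small glucose fall gives a negative ratio. Under the planned analysis:

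- the log model loses each participant-period without a positive ratio on both days, so the data are selected by the outcome itself;
- the untransformed model keeps every finite ratio, and a few with tiny denominators can set the estimate and its standard error.

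At stake is the interpretability of the secondary beta-cell endpoints, mainly the 10-minute ones.

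**Working it through.** **1. Can both definitions be applied?** Take an invented participant, with values at 0, 10 and 30 minutes.

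- Day -1: glucose 8.0, 8.5, 9.8 mmol/L; insulin 12, 16, 35 mU/L.
- Day 4: glucose 8.8, 9.5, 11.2 mmol/L; insulin 15, 21, 40 mU/L.

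| | Same-test, Day -1 | Same-test, Day 4 | Change | Between-day |
|---|---|---|---|---|
| 10 min | 4/0.5 = 8.0 | 6/0.7 = 8.57 | +0.57 | 5/1.0 = 5.0 |
| 30 min | 23/1.8 = 12.78 | 25/2.4 = 10.42 | -2.36 | 5/1.4 = 3.57 |

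The between-day version gives one number per period. There is then no Day -1 ratio to serve as covariate and no change in the ratio to analyse. Only the same-test definition fits the model.

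**2. How large is ΔG10?** The documents give no mean or SD. The nearest figure is the SAP rule that sets a missing pre-meal glucose to 92% of the next scheduled value. Assuming this factor describes the step from -15 to 10 minutes, mean ΔG10 = fasting glucose × (1/0.92 - 1) = fasting glucose × 0.087. The fasting range in inclusion criterion 2 (one route to eligibility) and the SAP conversion of 0.0555 give:

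- 126 mg/dL: 6.99 × 0.087 = 0.61 mmol/L
- 220 mg/dL: 12.21 × 0.087 = 1.06 mmol/L

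**3. How often is ΔG10 at or below zero?** Assuming normality, P = Φ(-mean/SD). The SDs are assumed. Cohort 1 has 24 participants × 2 days × 2 periods = 96 ratios.

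| Mean ΔG10 | SD 0.3 | SD 0.5 | SD 0.8 |
|---|---|---|---|
| 0.61 | 2.1% (2 of 96) | 11.1% (11 of 96) | 22.3% (21 of 96) |
| 1.06 | <0.1% (0 of 96) | 1.7% (2 of 96) | 9.3% (9 of 96) |

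**4. How often is the ratio at or below zero?** Assume ΔI10 is normal with mean 20 and SD 15, independent of ΔG10. Only mean/SD matters for the sign, so the insulin unit does not. Then q = P(ΔI10 ≤ 0) = Φ(-20/15) = 0.091. With p from step 3, P(ratio ≤ 0) = p(1 - q) + q(1 - p). At mean 0.61:

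- SD 0.3: 0.021 × 0.909 + 0.091 × 0.979 = 0.108
- SD 0.5: 0.111 × 0.909 + 0.091 × 0.889 = 0.182
- SD 0.8: 0.223 × 0.909 + 0.091 × 0.777 = 0.273

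That is about 11% to 27%. With ΔI10 mean 5 and SD 4 the simulated shares are 12%, 19% and 28%. Part of each share comes from the assumed ΔI10, not from the denominator.

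**5. What does the log model lose?** A participant-period needs a positive ratio on both days. Treating the days as independent, the usable shares are 0.892² = 80%, 0.818² = 67% and 0.727² = 53% for the three SDs.

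**6. What happens to the untransformed model?** Simulation with ΔG10 mean 0.61 and SD 0.5, and ΔI10 mean 5 and SD 4, gives a median ratio of about 6 with 1st and 99th percentiles of about -195 and +212. The SD in samples of 24 runs from about 14 to 202 (10th to 90th percentile). With ΔI10 mean 20 and SD 15, and ΔG10 mean 0.61, the two most extreme of 24 participants carry a median of about 80% of the sum of squares of the treatment contrast.

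**The case against.** **The definitions do not truly compete.** SAP 4.12.2 gives explicit steps, and the literal reading of 4.8 cannot be fitted. Section 4.8 may have been meant as the baseline for the ratio. This stands as far as it goes: the mismatch is a wording error in 4.8. The wording nevertheless names the components, so it needs correcting.

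**The rates are assumed.** This also stands. A reader might infer from the 30-minute meal allowance that glucose has barely moved at 10 minutes and that ΔG10 is often zero or negative. The documents do not show that. Their one relevant figure, the 92% factor, points to a mean rise of 0.61 to 1.06 mmol/L. At 1.06 with SD 0.3 the mean lies 3.5 SDs above zero and the denominator problem all but disappears. The factor comes from another study whose sampling times are not given, so it does not settle the matter either way.

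**Loss of participants can be overstated.** A reader might count only participants with all four ratios positive, which at mean 0.61 and SD 0.8 is 0.727⁴ = 28%. That is the least favourable case in the table. It assumes that the four ratios from one person are independent, and it ignores that the mixed model can use a single period.

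**30 minutes.** No figure above is for 30 minutes. The glucose rise should be larger there and the defect weaker, so these results do not support abandoning inference on ΔI30/ΔG30 or ΔC30/ΔG30.

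**Phase 2a.** These are secondary endpoints without multiplicity adjustment. That limits the consequence but does not make the log of a negative number usable.

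**Conclusion.** The point holds on the text. SAP 4.8 and 4.12.2 disagree on Δ. The model pair carried over from the primary endpoint is unsuitable for a ratio of two differences, and no rule covers non-positive values. The C-peptide ratios share the defect.

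The size is uncertain. If the 92% factor applies, and with an assumed SD of 0.3 to 0.8 mmol/L and normality, ΔG10 is at or below zero in under 0.1% to 22% of tests. At mean 0.61, with the assumed ΔI10 and independence, about 11% to 27% of 10-minute ratios are at or below zero. The problem is chiefly at 10 minutes. The primary analysis and the Cohort 1 sample size are unaffected. The change should be made, but it is not critical to the trial's main conclusion.

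**What to change.** 1. Correct SAP 4.8 so that Δ is the increment within one meal test, with the Day -1 ratio as baseline for the change in the ratio. State that the -15 minute sample serves as time 0 for the ratios; the SAP now says so only for AUC.
2. Do not apply the log model to these ratios, and drop the percent change that goes with it.
3. Base the treatment comparison on a rank-based or other robust two-period cross-over analysis of the change in the ratio.
4. Pre-specify the handling of ΔG at or below zero. Ranking limits the weight of an extreme ratio but does not give meaning to one with a negative denominator. Report the count of such values by treatment and day.
5. Summarise the ratios by median and quartiles.
6. Optionally add insulin and C-peptide AUC(0-30) over glucose AUC(0-30), on the log scale, as a supportive analysis. These ratios are positive and use samples already taken. They include basal levels and so measure something different. They should not replace the increment ratios, which are protocol secondary endpoints.

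The cost is SAP text and programming, with no new samples. Protocol 9.4.2.2 foresees a linear or mixed model here, so a rank-based method should be recorded in SAP 4.15. The effect measure will be less familiar.
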